**12.4.2. Age**

- Age: age at the reference activity is computed as the number of units between the date of birth and the reference activity, expressed in months/years.

When age at reference activity is to be displayed in months/years, it will be calculated as the number of complete calendar months/years between the date of birth and the date of reference activity. For example:

- DOB = 10JUN2017, Date of vaccination = 09JUL2018 -> Age = 12 months
- DOB = 10JUN2017, Date of vaccination = 10JUL2018 -> Age = 13 months
- DOB = 10SEP1983, Date of reference = 09SEP2018 -> Age = 34 years
- DOB = 10SEP1983, Date of reference = 10SEP2018 -> Age = 35 years

**12.4.3. Time interval**

Time interval between 2 visits is expressed in days. It is the number of days between the 2 visit dates. Therefore, the time interval is of 0 day if the 2 visit dates are the same.

Time interval expressed in years will be computed as follows: time interval expressed in days/365.25.

#### 12.4.4. Duration

Duration of an event is expressed in days. It is the number of days between the start and the stop dates + 1. Therefore, duration is 1 day for an event starting and ending on the same day.

#### 12.4.5. SDC confirmed by RT-qPCR

A SDC will be considered as confirmed by RT-qPCR if at least one Dengue Virus Type 1, 2 3 or 4 RNA result is POS.

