**Table 5 Volume of whole blood for study related testing (Amended: 24 July 2017)**

Age group	Type of Visit			
	Visits 1, 2 and 3	SDC – first visit		Cases where dengue is ruled out
		Early presenter	Late Presenter	
6 months to <2 years	3.5 ml	3.5 ml	3.5 ml	3.5 mL
2-50 years	10 ml	10 ml	10 ml	9 mL

If blood collection is not feasible, a finger prick test may alternatively be performed for testing with a IgM/IgG/NS1 ICT.

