**7. STATISTICAL ANALYSES**

SAS software will be used for statistical analysis.

Note that data derivation rule and statistical methods are described in Section 12 and will not be repeated below.

Continuous variables will be summarized with number of non-missing observations, mean, standard deviation (SD), median, minimum, maximum, 25th and 75th percentiles. Categorical variables will be summarized with frequency tables; numbers and percentages for each level will be given.

If an elimination code 900 is attributed, then all the analyses planned to be done on the Total cohort will be done on the Total cohort without subjects with code 900, except Template 5 from EPI-DENGUE-007 BOD (200318) TFL (24-MAY-2019) DRAFT.

The final analysis will be performed on the following study sites using data up to the specified study visits covered up to study termination:

Study sites name	Number of enrolled subjects	Study visits covered at study termination	Dengue season covered at study termination
Mexico	350	Visit 1 to Visit 3	2017, 2018
Philippines	500	Visit 1 to Visit 2	2018

The laboratory results (POS/NEG/IR=invalid result/EQV=equivocal (i.e. level of measured Dengue IgG Ab is not enough to conclude of a Dengue infection)) will be available at the scheduled visits for the following tests:

- Dengue Virus Ab.IgG by ELISA (v\_id= 3789.005) will be available at Visit 1 for Mexico site
- Dengue Virus Ab.IgG by ELISA (v\_id= 3789.005) will be available at Visit 1 and 2 for Philippines site

The laboratory results (POS/NEG/IR) will be available in case of SDC, at first visit, for the following tests:

Assays	Method	Early presenters	Late presenters
DENV RT-qPCR: 
 
• Dengue Virus Type 1 RNA (v_id= 3415.005)
 
• Dengue Virus Type 2 RNA (v_id= 3415.006)
 
• Dengue Virus Type 3 RNA (v_id= 3415.007)
 
• Dengue Virus Type 4 RNA (v_id= 3415.008)
 
	RT-qPCR	Yes	Yes
DENV NS1	RAPIDIMM	Yes	Yes
Anti-DENV IgM	RAPIDIMM	Yes	Yes
Anti-DENV IgG	RAPIDIMM	Yes	Yes
Hematology / Biochemistry		Yes	Yes

RAPIDIMM = rapid immunochromatographic assay

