### 7.4. Analysis of incidences

The analyses will be performed on the ATP cohort.

The following analyses will be performed by study site and overall:

- Incidence proportion of RT-qPCR confirmed symptomatic dengue infection during the study period.
- Incidence proportion of virologically confirmed symptomatic dengue infection during the study period.
- Incidence proportion of probable symptomatic dengue infection during the study period.
- Incidence proportion of virologically confirmed or probable symptomatic dengue infection during the study period.
- The numerator will be the number of subjects with at least one specified event reported during the study period. The denominator will be the number of subjects in the ATP cohort.

95% CI accounting for clustering effect will be computed on all estimated incidence proportions. The method for estimating the CIs is described in Section 12.1.

- The proportion, with 95%CI, of subjects with Dengue Virus Ab.IgG positive result (ELISA) at Visit 1 will be tabulated by study site and age category.

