## 11. LIST OF FINAL REPORT TABLES, LISTINGS AND FIGURES

Refer to the document entitled EPI-DENGUE-007 BOD (200318) TFL (24-MAY-2019) DRAFT.docx.

The following group names will be used for the statistical analyses.

- Age categories:

Group order in tables	Group label in tables	Group definition for footnote
1	6 months-<12 months	From the 6th month birthday up to and including the day before the 1st year birthday
2	1-4 years	From the 1st year birthday up to and including the day before the 5th year birthday
3	5-8 years	From the 5th year birthday up to and including the day before the 9th year birthday
4	9-17 years	From the 9th year birthday up to and including the day before the 18th year birthday
5	18-50 years	From the 18th year birthday up to and including the day before the 51th year birthday

- Study sites (named center in the database):

Group order in tables	Group label in tables	Group definition for footnote
1	Mexico	No footnote
2	Philippines	

- Ad-hoc visits:

Group order in tables	Group label in tables	Group definition for footnote
1	Non SDC	Ad-hoc visits without suspicion of dengue
2	SDC	Ad-hoc visits with suspicion of dengue

- Symptomatic dengue confirmation status:

Group order in tables	Group label in tables	Group definition for footnote
1	Virologically confirmed	Symptomatic dengue cases confirmed by RT-qPCR or NS1
2	Probable	Probable symptomatic dengue cases
3	Other SDC	Symptomatic dengue cases not classified as virologically confirmed or probable

- Early/late presenter classification:

Group order in tables	Group label in tables	Group definition for footnote
1	Early presenter	Suspected dengue cases presenting at the health care facility within 5 days of symptoms onset
2	Late presenter	Suspected dengue cases presenting at the health care facility 6 days or more after symptoms onset

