**12.3. Handling missing data**

No data handling will be performed in case of missing data.

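### The RT-qPCR-confirmed proportion is a minimum: suspected cases without a valid RT-qPCR count as non-events, and the SAP text neither tabulates nor bounds them

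*SAP*

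**What the plan says.** - **Event rule (SAP 12.4.5).** An SDC is "confirmed by RT-qPCR if at least one Dengue Virus Type 1, 2 3 or 4 RNA result is POS". No rule covers an invalid or missing RNA result.
- **Numerator and denominator (SAP 7.4).** On events, the section says: "The numerator will be the number of subjects with at least one specified event reported during the study period". It then sets no condition on having been tested: "The denominator will be the number of subjects in the ATP cohort". Under SAP 5.1 and 5.2.2, ATP membership depends only on consent or fraud (code 900) and eligibility (code 2010), not on testing.
- **Missing data (SAP 12.3).** "No data handling will be performed in case of missing data".
- **Possible results (SAP 7).** "The laboratory results (POS/NEG/IR) will be available in case of SDC, at first visit, for the following tests". RT-qPCR is one of these tests, and IR means an invalid result.
- **Ways to have no RT-qPCR.** The note to Protocol Table 5 reads: "If blood collection is not feasible, a finger prick test may alternatively be performed for testing with a IgM/IgG/NS1 ICT". Protocol 7.5.4 foresees only retrospective clinical data for subjects seen at non-study facilities. It also says RT-qPCR is not run on late presenters, whereas the assay table in SAP 7 marks it as available for them. Those two passages must be reconciled.
- **Outputs.** SAP 7.3 lists every SDC with early/late class, sample date, laboratory results and classification, and summarises clinical features by confirmation class. SAP 11 defines the residual class, *Other SDC*, as "Symptomatic dengue cases not classified as virologically confirmed or probable".

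**The concern.** A missing endpoint and a negative endpoint are scored alike, so the error can only run downward. It may also differ between the two sites if sampling success differs, and SAP 7.4 reports the proportion by site. SAP 10 itself cites the low number of cases as its reason for dropping sub-analyses. With so few events, one or two untested positives would visibly move the headline figure. A reader of the planned primary result could not tell whether it rests on nearly complete testing.

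The same gap runs through *Other SDC*, which combines fevers that tested negative with fevers that could not be classified. One group is especially unclear. In SAP 6.2.3 the not-performed option for RT-qPCR is tied to late presenters. An early presenter with an invalid or absent RT-qPCR, a non-positive NS1 and positive serology therefore has no clear class and may fall into *Other SDC*. The footnote then calls the whole class symptomatic dengue cases, although SDC stands for suspected dengue case in the SAP's own abbreviations.

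**Working it through.** **1. How each RT-qPCR status is scored (SAP 12.4.5, 7.4, 12.3)**

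| RT-qPCR status of the SDC | Primary numerator | Denominator | Other route into a case class |
|---|---|---|---|
| POS | 1 | 1 | already virologically confirmed |
| NEG | 0 | 1 | NS1, or probable by serology |
| IR | 0 | 1 | NS1; probable class unclear |
| Not done | 0 | 1 | NS1; probable if late presenter, otherwise unclear |

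The last three rows are identical for the primary endpoint.

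**2. The protocol's planning figure (Protocol 10.2) reproduces.** With 5% yearly dropout, 1750 subjects become 1662.5 and then 1579.4.
- Person-years: (1750 + 1662.5)/2 + (1662.5 + 1579.4)/2 = 3327.2.
- Rate: 0.7 × 8 + 0.3 × 5 = 7.1 per 1000.
- Cases: 3327.2 × 0.0071 = 23.6, which the protocol rounds to 24.
- Exact Poisson 95% CI: 4.5 to 10.6.
- Normal CI with design effect 1.8: 7.1 ± 1.96 × √(1.8 × 0.0071/3327.2) × 1000, giving 3.3 to 10.9.

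**3. Scale in the enrolled cohort.** Enrolment was 350 in Mexico and 500 in the Philippines (SAP 7). Assume the protocol's rates and dropout, with two years in Mexico and one in the Philippines.
- Mexico: 350 × (1 + 0.95)/2 + 350 × (0.95 + 0.9025)/2 = 665.4 person-years, or 4.7 cases.
- Philippines: 500 × (1 + 0.95)/2 = 487.5 person-years, or 3.5 cases.
- Total: 1152.9 person-years × 0.0071 = 8.2 confirmed cases, or 0.96% of 850.

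On that scale one case is about 12% of the total (1/8.2), 21% of Mexico's count (1/4.7) or 29% of the Philippines' count (1/3.5). With all 850 enrolled standing in for the ATP cohort, one subject is 1/850 = 0.12 percentage points.

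**4. Size of the shortfall.** Let *u* be the share of SDC without a valid RT-qPCR. Let *q* be the positivity those SDC would have had, relative to tested SDC. Treating SDC as one per subject:

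observed / fully tested = (1 − u) / [(1 − u) + u·q]

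The documents give neither *u* nor *q*, so both are assumed. At u = 0.2 and q = 1.5, for example, 0.8/(0.8 + 0.3) = 0.727, a shortfall of 27%.

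| u | q = 0 | q = 0.5 | q = 1 | q = 1.5 |
|---|---|---|---|---|
| 10% | 0% | 5% | 10% | 14% |
| 20% | 0% | 11% | 20% | 27% |
| 30% | 0% | 18% | 30% | 39% |

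**5. Bounds that need no value of *q*.** Let A be the ATP subjects and P those with a POS episode. Let U be those with no POS episode but at least one SDC lacking a valid RT-qPCR. The fully tested proportion lies between P/A, which is the planned estimate, and (P + U)/A.

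**The case against.** The strongest reply is that the endpoint is RT-qPCR-confirmed infection, and a subject without a positive result is correctly not confirmed. SAP 7.4 also reports virologically confirmed, probable, and combined proportions, so an NS1-positive case without RT-qPCR is still counted there. A reader might infer that untested cases are treated as dengue-free throughout. The documents do not support that; the omission is confined to the RT-qPCR numerator and to unclassifiable cases.

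A reader might also infer that the primary result is low by exactly the untested share. That holds only if untested SDC would test positive as often as tested ones (q = 1), and nothing in the documents establishes this. Nor should the 7.1 per 1000 be discounted as if it were a true rate. Protocol 10.2 presents it as a rate of confirmed cases, so the 8.2 above is a design-stage scale only.

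There is no evidence that the untested share was large. IR is a result code, not proof that invalid results occurred. The finger-prick wording quoted is Amendment 3 text, while SAP 1 and 2.1 place Mexico under Amendment 1. The amendment history in Protocol Appendix C shows the sentence was limited to young children with SDC until Amendment 3 removed that limit, so the broad route did not govern 350 of the 850 subjects.

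Finally, the share is not concealed. The SDC listing gives sample date and results for each case, and with few cases a hand count is practical. A table in the separate TFL document cannot be ruled out. SAP 8 makes all analyses descriptive and no test-negative comparison is planned, so the *Other SDC* point is one of classification and labelling.

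These points limit the size and reach of the concern. They do not change the scoring rule, and a listing does not qualify the headline estimate.

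**Conclusion.** The point stands in a limited form. As specified, the primary proportion is a lower limit on what RT-qPCR testing of every SDC would have shown. Any error from untested or invalid cases is downward, and its size cannot be computed from the documents. If 20% of SDC were untested, the shortfall would be 0% to 27% for a relative positivity of 0 to 1.5; if none were, it would be zero. The SAP text plans neither a count of untested SDC nor a bound. This is a cheap improvement to how the result can be read, not evidence that the result is wrong.

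**What to change.** 1. **SAP 7.3:** tabulate SDC by RT-qPCR status (POS, NEG, IR, not done), by site and early/late class. This would also show what was actually done for late presenters.
2. **SAP 7.4:** describe the primary proportion as a minimum. Counting each subject once, show P/A (no untested SDC positive) and (P + U)/A (all untested SDC positive). The SAP 12.1 model can be rerun on the recoded outcome for the upper bound. One pooled point estimate at the positivity of tested SDC is optional. Imputation stratified by site and NS1 result is not advisable: the cells would be nearly empty, and the resulting fractional events have no interval method in the SAP.
3. **SAP 11:** split *Other SDC* into laboratory-negative SDC and SDC not classifiable because of missing or invalid tests. Change the footnote to begin *Suspected dengue cases*.

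The inputs are already in the SDC listing. The cost is one small table, one extra bound and a relabelled class, with a less tidy range around the headline figure. If untested SDC outnumber confirmed cases the upper bound will be wide, which the reader should know.

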#### 12.4.6. Classification of severity of dengue

**Criteria for dengue with warning signs (WHO 2009):** at least one of the following should be present (i.e. criteria box ticked in the eCRF):

- Abdominal pain or tenderness,
- Persistent vomiting (three or more emesis in a period of one hour, or five or more in a period of six hours),
- Clinical fluid accumulation (peri-orbital, facial or lower limb oedema as reported by the study physician, or pleural effusion, ascites or gall-bladder wall thickening  $\geq 3$  mm as observed via X-ray radiography or ultrasonography),
- Mucosal bleed (any of the following: hemoptysis, epistaxis, gingival bleeding, melena, hematemesis, hematuria, menorrhagia, vaginal bleeding, or subconjunctival hemorrhage as observed by a study physician or reported by the patient),
- Liver enlargement (liver enlarged  $>2$  cm below the edge of the ribs as palpated by a study physician),
- Increase in HCT concurrent with rapid decrease in platelet count (interpreted as any HCT  $>20\%$  over baseline with platelet  $50,000/\text{mm}^3$ ),
- Lethargy (Glasgow coma scale score  $<15$  for children aged 5 years or more or Blantyre coma scale  $<5$  for children under 5, as evaluated by a study physician) and restlessness.

**Criteria for severe dengue (WHO 2009):** dengue with at least one of the following criteria (i.e. criteria box ticked in the eCRF):

- Severe Plasma Leakage leading to Shock (DSS), Fluid accumulation with respiratory distress,
- Severe Bleeding,
- Severe organ involvement;
- Liver: AST or ALT  $\geq$  1000 IU/L,
- Central nervous system: impaired consciousness,
- Failure of heart and other organs.

#### **12.4.7. Fever at the visit**

The status of fever at the visit for suspicion of dengue will be derived from the fever tick box of the eCRF from the list of main signs.

#### **12.4.8. Safety**

For analysis of serious adverse events related to study procedures, all enrolled subjects will be considered. Subjects who did not report the event will be considered as subjects without the event.

